**14-April-2020**

### **STATEMENT OF COMPLIANCE**

The study will be conducted in accordance with the International Conference on Harmonization guidelines for Good Clinical Practice (ICH E6) and the Code of Federal Regulations on the Protection of Human Subjects (45 CFR Part 46). All personnel involved in the conduct of this study have completed Good Clinical Practice (GCP).

## LIST OF ABBREVIATIONS

Term	Explanation
ABI	Ankle-Brachial Index
BMI	Body Mass Index
CEAP	Clinical-Etiology-Anatomy-Pathophysiology classification
CFR	Code of Federal Regulations
CVI	Chronic Venous Insufficiency
DUS	Duplex Ultrasound
DVT	Deep Venous Thrombosis
EC	Ethics Committee
GCP	Good Clinical Practices
GSV	Great Saphenous Vein
IPV	Incompetent Perforator Vein
IV	Intravenous
PI	Perforator Incompetency
PV	Perforator Vein
RF	Radiofrequency
RFA	Radiofrequency Ablation
SEPS	Subfascial Endoscopic Perforating Vein Surgery
SFJ	Sapheno-Femoral Junction
SPJ	Sapheno-Popliteal Junction

## Section 3 – INVESTIGATION PLAN

### CLINICAL PROTOCOL SUMMARY

Title:	Investigator Initiated Safety Study Using the Venclose Vestico (commercial name TBD) Radiofrequency (RF) Ablation System for the Treatment of Incompetent Perforator Veins (IPVs)
Synopsis:	
An Investigator Initiated study conducted to evaluate the safety of the Venclose digiRF Generator with Vestico Catheter System (“Vestico”) treating incompetent perforator veins (IPVs). The study will be conducted in compliance with IDE requirements under local IRB approval(s). Study data will be summarized and submitted to FDA in a premarket notification once all subjects have completed 30-day follow-up.
 
Venclose’s venous ablation technology is already cleared by FDA for use in treating chronic venous insufficiency, especially treating saphenous and branching veins, and has been in clinical practice since 2017 with extremely low adverse events. The study’s working hypothesis is that using the Venclose Vestico Catheter System will safely treat incompetent perforator veins (IPVs) without resulting in any adverse outcomes related to use of the device.
 
A physician with extensive clinical background and experience in treating vascular and venous diseases and a medical license to practice in the United States will use the Vestico device to treat a minimum of 30 IPVs on at least twenty (<math>\geq 20</math>) and a maximum of thirty (<math>\leq 30</math>) subjects.

Description of Intervention:	Following informed consent, the physician operator will gain access to the IPV in the leg using ultrasound guidance. The Vestico device will be inserted into the vein lumen also with ultrasound imaging guidance and the target treatment position confirmed. After providing local anesthesia to the vein and surrounding tissues, the Vestico device will be activated to deliver the thermal ablation energy to the vessel. Once the treatment cycle has been completed the device will be withdrawn and closure confirmed with duplex ultrasound. A bandage and compression hose will be applied. The patient will then immediately ambulate.
Number of Sites:	Single Site
Objectives:	

1) The study’s working hypothesis is that using the Venclose Vestico Catheter System for treating incompetent perforator veins (IPVs) will not result in significant adverse outcomes related to use of the device.

- 2) The study will be conducted in compliance with IDE requirements and labeling (21 CFR 812.2(b)) under local IRB approval(s).
- 3) Multiple limbs and IPVs may be treated. All IPVs treated will be followed according to the study schedule.

**Population:**

At least twenty ( $\geq 20$ ) and a maximum of thirty ( $\leq 30$ ) ambulatory subjects diagnosed with Incompetent Perforator Veins (IPVs) who meet the inclusion and exclusion criteria, both males and females over the age of 18, will be enrolled at one clinic.

**Primary Endpoints:**

- 1) Safety - Procedure related adverse events (AE), serious adverse events (SAE), adverse device effects (ADE), serious adverse device effects (SADE) and unanticipated adverse device effects (UADE) will be monitored 3 days, 15 days (+/- 3 days), and 30 days (+/- 3 days) post-procedure and analyzed for acceptability post study .

Monitored events include:

- Edema
- Skin changes
- Venous ulcers
- Deep vein thrombosis
- Superficial vein thrombosis
- Pulmonary embolism
- Venous thromboembolism
- Skin burn
- Thermal injury of adjacent tissues
- Paresthesia
- Infection/cellulitis
- AV Fistula
- Need for re-operation
- Death

- 2) Effectiveness - Technical success, defined as successful access and entry into the IPV to be ablated and the ability to deliver the intended energy to the target vein segment, will be evaluated.

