### **Duplex Ultrasound:**

Duplex ultrasound is a non-invasive evaluation of blood flow through the arteries and veins. This test provides information to help the vascular interventionist make a sound diagnosis and outline an appropriate treatment plan. Accuracy is critical, so ultrasound testing should be performed by a credentialed sonographer in an experienced vascular laboratory. There are typically no side effects or complications associated with duplex ultrasound examinations.

Pregnant women, children and adolescents have been excluded from the study.

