##### Outcome Measures

###### Primary Endpoints:

- 1) Safety - Procedure related adverse events (AE), serious adverse events (SAE), adverse device effects (ADE), serious adverse device effects (SADE) and unanticipated adverse device effects (UADE) will be monitored and analyzed for acceptability post study.

Monitored events include:

- Edema
- Skin changes
- Venous ulcers
- Deep vein thrombosis
- Superficial vein thrombosis
- Pulmonary embolism
- Venous thromboembolism
- Skin burn
- Thermal injury of adjacent tissues
- Paresthesia
- Infection/cellulitis
- AV Fistula
- Need for re-operation
- Death

- 2) Effectiveness - Technical success, defined as successful access and entry into the IPV to be ablated and the ability to deliver the intended energy to the target vein segment, will be evaluated.

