#### **B. Protocol**

- i. Enrollment: At least twenty ( $\geq 20$ ) and a maximum of thirty ( $\leq 30$ ) subjects requiring thermal ablation will be asked to participate in this study. Exclusion criteria will include any factors excluding a patient from having RFA (e.g. medical conditions, psychological conditions, or vascular conditions) and/or exclude the use of the Vestico Device (See Section 4 for detailed inclusion/exclusion criteria).
- ii. Clinical Procedures: There will be an informed consent/consultation visit and an intervention visit. A pre-operative Duplex Ultrasound imaging will be obtained prior to or during the consultation visit. The Vestico device will be used to treat IPVs during the intervention visit. Safety assessments and pre- and post-treatment Duplex Ultrasound imaging will be obtained measuring reflux during the primary intervention. Safety assessments and post-operative Duplex Ultrasound images will be obtained within 3 days after the intervention. All subjects will be followed up at 3-days, 15-days and 30-days post-operatively for a safety assessment and Duplex Ultrasound. No further study intervention, study visits or study-specific data collection will follow the 30-day follow-up. The subject population will be patients in need of treatment for Chronic venous insufficiency (CVI) and disease due to IPVs.
- iii. The Investigator proceeds with the Vestico Device procedure and will take a post-operative Duplex Ultrasound Scan following the ablation procedure.
- iv. Data and Imaging Collection and Study Monitoring: On the day of surgery, Screening and Baseline Visit Case Report Forms (CRFs) will be completed by the Investigator or their delegate. The clinical study monitor will confirm that Pre- and Post-Operative Duplex Ultrasound Scans are taken.
- v. Analysis: The treatment plan, including the pre-operative Duplex Ultrasound Scan, and post-operative Duplex Ultrasound Scan images are collected by the clinical study monitor. Cessation of flow and cessation of flow reflux through the perforator vein(s) will be recorded, thoroughly investigated, documented and included in the study analysis. All adverse events related to the device will be handled and reported to regulatory authorities as per this study protocol.

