#### **D. Data Collection**

Data will be collected using case report forms (CRFs). The following describes the data being collected:

- Imaging and surgical preplanning information
- De-identified subject data (e.g. age, gender, medications and medical conditions)
- Device related data
- Surgical site data (e.g. location), blood flow, etc.
- Surgical Information (date and reason for the surgery, complications)
- Duplex Ultrasound Scans from pre- and immediately post-intervention.
- All adverse events

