#### **E. Investigators**

One investigator with a wide range of endovascular interventional experience and his assistants will be trained on the protocol, investigator and sponsor responsibilities, study procedures and the instructions for use of the Vestico device. (See Appendix A). The investigators and staff will be certified with GCP training.

A qualified clinical study monitor will verify data collection.

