## 4 STUDY ENROLLMENT AND WITHDRAWAL

### 4.1 Subject Inclusion Criteria

In order to be eligible to participate in this study, an individual must meet all of the following criteria:

1. Patient is  $\geq 18$  years.
2. IPVs to be treated have an outward flow duration of  $\geq 0.5$  seconds immediately after release of manual distal compression with patient standing or in Reverse Trendelenburg.
3. IPV(s) to be treated have a diameter of  $\geq 3.5$  mm located caudal edge of ankle.
4. Has been diagnosed with refractory symptomatic disease attributable to the IPV to be treated.
5. Is able to ambulate.
6. Is able to comprehend and has signed the Informed Consent Form (ICF) to participate in the study.
7. Is willing and able to comply with the Clinical Investigation Plan and follow-up schedule.

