## **6.6 3-day Post-Intervention Safety Assessment**

Follow-up Visit (3-days post-intervention)

- Document all adverse events, if any
- Post-operative Duplex Ultrasound Scan (same day or within 3 days of 3-day Follow-up)

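### The primary safety endpoint is worded as procedure-related events, yet the plan names no assessor, criteria or independent review for relatedness, although all adverse events are collected

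*Combined protocol and SAP*

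**What the plan says.** - **Endpoint.** Item 1 of the Primary Endpoints in the Clinical Protocol Summary, repeated in Section 3.1, begins "Procedure related adverse events (AE), serious adverse events (SAE), adverse device effects (ADE" and goes on to serious and unanticipated device effects. In Section 3.1 these "will be monitored and analyzed for acceptability post study". Fourteen event types are listed. No count, rate or acceptance threshold is given.
- **Collection.** Section 3.2 D lists "All adverse events" among the data collected. The 3-day visit (Section 6.6) has the instruction "Document all adverse events, if any", and Sections 6.7 and 6.8 repeat it for 15 and 30 days. None of these carries a relatedness condition.
- **People.** Section 3.2 E plans "One investigator with a wide range of endovascular interventional experience", with assistants. Under Section 8.2 the investigator asks about events at visits, and under Section 12.6 the Principal Investigator approves each case report form.
- **Relatedness.** The only definition is in Section 8.1.1, as part of what makes an unanticipated problem. The only mention of the investigator's opinion on events there concerns what goes to the IRB.
- **Oversight.** The monitor (Sections 9 and 10) checks errors, missing data and compliance. No role in judging events is described, and no events committee is set up.
- **Analysis.** Section 11.3, item 4, foresees a post-hoc review of adverse events without a relatedness limit.
- **Population.** Section 4.1, criterion 4, reads "Has been diagnosed with refractory symptomatic disease attributable to the IPV to be treated". Section 2.1 names edema, skin changes and ulcers as the way advanced disease shows itself.

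**The concern.** Collection is unfiltered and the endpoint wording is filtered, so someone must sort events into related and unrelated before the primary safety result exists. The plan leaves that step undefined: no assessor, no criteria and no independent check. There is no comparator to show the background rate, and no masking is described.

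The sorting is hardest where the disease and the complication look alike. Edema, skin changes and venous ulcers are monitored events. They are also signs of advanced disease in Section 2.1, and Section 2.3.2 lists ulcer healing and less edema among the hoped-for benefits. An ulcer that persists or worsens could be recorded as disease, as lack of benefit or as a procedure event, and the plan has no rule for choosing.

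The data are meant for a premarket notification. With 20 to 30 subjects, a few attribution decisions could move the reported rate visibly, and a reader of the submission could not tell how they were made.

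**Working it through.** **Is there a figure of the plan's own to reproduce?** No. Section 11.3 states that there is no formal sample size calculation, and the safety endpoint has no rate or threshold. The figures below only show scale.

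**Step 1: who decides, and how?** Setting the sections side by side:

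| Question | Where the plan comes closest | What it covers |
|---|---|---|
| Who asks about events? | 8.2 | The investigator |
| Who signs off the forms? | 12.6 | The Principal Investigator |
| Who judges relatedness for the primary endpoint? | Nowhere | Not stated |
| By what criteria? | 8.1.1 | Unanticipated problems only |
| Who reviews independently? | 9, 10 | Data quality and compliance, not causality |

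With one investigator planned and nobody else given the task, the treating investigator is the likely default. That is an inference.

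**Step 2: how many event types are open to a disease reading?** Edema, skin changes and venous ulcers are 3 of the 14 listed types. Several of the rest, such as death, pulmonary embolism, deep vein thrombosis and AV fistula, leave less room for a choice between disease and procedure.

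**Step 3: how far does one decision move the result?** Inputs: n = 20 and n = 30, the enrolment limits in Section 11.3. Assumption: the summary is the proportion of subjects with at least one event. One subject reclassified moves it by 1/n:

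- n = 20: 1/20 = 5.0 percentage points
- n = 30: 1/30 = 3.3 percentage points

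Exact (Clopper-Pearson) 95% limits for x subjects out of n are the 0.025 quantile of Beta(x, n − x + 1) and the 0.975 quantile of Beta(x + 1, n − x). For x = 0 the lower limit is 0 and the upper limit is 1 − 0.025^(1/n).

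| Subjects with a related event | n = 20 | n = 30 |
|---|---|---|
| 0 | 0% (0 to 16.8%) | 0% (0 to 11.6%) |
| 1 | 5.0% (0.1 to 24.9%) | 3.3% (0.1 to 17.2%) |
| 2 | 10.0% (1.2 to 31.7%) | 6.7% (0.8 to 22.1%) |
| 3 | 15.0% (3.2 to 37.9%) | 10.0% (2.1 to 26.5%) |

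**Step 4: an assumed example.** Suppose three subjects have an adverse event; this number is not from the documents. Calling none of them related gives 0%, with an upper limit of 16.8% at n = 20 or 11.6% at n = 30. Calling all three related gives 15.0% or 10.0%. The same data support either row, depending on a judgment that the plan does not define.

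**The case against.** The strongest reply is that the plan is less restrictive than the opening words of the endpoint suggest. Grammatically, the procedure-related condition may apply only to the first item or two in the list. The device-effect categories are device-related by name, and the 14 monitored events carry no separate relatedness condition. Section 11.3 already foresees a review of adverse events without a filter. The working hypothesis concerns outcomes related to the device, so some attribution is unavoidable and an all-cause table alone would not address it. The intervals show that the study is small; they do not estimate how often events would be misattributed.

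Much of this stands. It does not settle the matter, because the Section 11.3 review is post hoc with no table specified, and uncertainty over what the condition covers is itself a reason to fix the wording.

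Three stronger readings are tempting and are not supported:

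- A reader might infer that the operator is assigned the relatedness decision. No section says so, and Sections 5.2 and 5.4 speak of investigators in the plural. The documented gap is that nobody is named.
- A reader might infer that one reclassified event would settle the study's conclusion. There is no threshold. The hypothesis also appears in two forms: the Synopsis and the opening of the Clinical Protocol section exclude any device-related adverse outcome, while the Objectives and Section 2.2 exclude only significant ones. Under the second form, one reclassified edema need not change the conclusion.
- A reader might infer that enrolled limbs generally show edema, skin changes or ulcers at baseline. Section 2.1 describes advanced disease in the population, and criterion 4 requires symptomatic disease without naming those signs. How many subjects would have them is unknown.

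**Conclusion.** The concern holds in this form: the primary safety endpoint is worded around procedure-related events, all adverse events are collected, and the plan does not say who judges relatedness, how, or under what review. The judgment would by default rest with the sole treating investigator in a study without a comparator.

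The effect is 5.0 percentage points per reclassified subject at n = 20 and 3.3 at n = 30. This assumes a subject-level proportion, which the plan does not itself define. The direction and frequency of any misattribution cannot be estimated from the documents.

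This does not invalidate the study. It leaves the main safety statement resting on an undefined judgment when a less attribution-dependent summary could be built from adverse events and examinations already recorded, so it should be changed before the data are reviewed.

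**What to change.** Reword the primary safety endpoint in the Clinical Protocol Summary and Section 3.1 as follows.

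1. **Primary summary:** all adverse events after the procedure, whatever their attribution. This includes every listed monitored event that is new or worse than the physical and clinical examination already recorded at the Baseline visit (Section 6.5). Report the number of subjects with at least one event, with an exact 95% interval.
2. **Beside it:** the procedure-related and device-related subsets, using the relatedness definition already in Section 8.1.1 and naming who applies it. This keeps the device-related hypothesis assessable.
3. **Section 11.3, item 4:** refer to this table, so that the all-event review is planned and not only post hoc.

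**Cost:** mainly endpoint and table wording, with no added staff, visits or subjects. The headline rate may be higher and will include some unrelated events; the related columns let a reader see this. The change reduces discretion without removing it. The investigator would still judge what is new or worse, and neither Section 3.2 D nor Section 6.5 lists a grading of edema, skin changes or ulcers, so the Baseline form must record these signs clearly enough for the comparison to be made.

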**Secondary Endpoints:**

- 1) The acute ablation success endpoint is defined as complete lack of flow or IPV disappearance in the treated segment (vessel occlusion). Success will be measured by Duplex Ultrasound imaging performed 3 days, 15 days (+/- 3 days), and 30 days (+/- 3 days) post-procedure.
- 2) Presence of reflux in the treated IPV will be recorded at each time point (3, 15, and 30 days post intervention) and an overall

absence of reflux rate (i.e. reflux free rate) will be documented at each follow-up time point

[figure not shown]
**Subject Participation Duration:**

Five Visits: An Informed Consent / Consultation visit; Intervention visit; routine follow-up within 3 days post-intervention, follow-up visit at 15 days post-intervention, and final follow-up visit at 30 days post-intervention. Total duration: three - five hours.

**Study Duration:** Three to four months

CONFIDENTIAL

## 2 INTRODUCTION

### 2.1 Background Information

As stated by the Society of Vascular Surgery in 2011, in the Western adult population, the prevalence of varicose veins is > 20% (range, 21.8%-29.4%), with about 5% (range, 3.6%-8.6%) have advanced disease manifesting as lower extremity venous edema, skin changes or venous ulcerations. Active venous ulcers are present in up to 0.5%, and between 0.6% and 1.4% have healed ulcers. On the basis of estimates of the San Diego epidemiologic study, more than 11 million men and 22 million women between the ages of 40 and 80 years in the United States have varicose veins, and 2 million adults have advanced CVD, with skin changes or ulcers. The incidence of post-thrombotic venous ulcers has not changed in the past two decades for women, and it recently increased in men. In the United States each year, at least 25,000 patients receive a new diagnosis of venous ulcers. Chronic venous insufficiency (CVI) is prevalent worldwide.

As the primary established mode of endovenous therapy for CVI in the US for over 20 years, thermal ablation for venous reflux via a time-temperature based thermal injury produces collagen denaturation and vein diameter reduction resulting in safe and efficacious fibrotic occlusion of the vessel.

Incompetent perforator vein treatment using the Venclose Vestico Catheter System uses the same mechanism of action (MOA) as the Medtronic RFS procedure cleared by FDA (K number) for IPVs as well as the same MOA as the Venclose EVSRF procedure previously cleared by the FDA (K number) for thermally ablating Saphenous reflux. The only difference between the RFS and the Vestico/EVSRF technology is the mode of thermal energy delivery which is bipolar energy delivered directly to the patient tissues for RFS vs. patient isolated resistive heating for the Vestico/EVSRF technology. Thermal energy (i.e., heat energy; time-at-temperature) is what effects successful collagen denaturation and vessel occlusion. Both bipolar and resistive technologies accomplish the same result (i.e., both impart heat energy to occlude the vessel). In the case of the Vestico system, the resistive heating technology is inherently safer since the patient (i.e., patient's tissues) is not used as part of the electrical circuit which is the case for the FDA cleared RFS device currently in use today. Additionally, resistive heating technologies like the Venclose EVSRF and Medtronic ClosureFAST technologies have proven to be the standard of care for much larger diameter vessels than required for treating perforator veins. Consequently, based on the understanding of the thermal effects on collagen, and on the typical size of the target vein anatomy, these resistive heating technologies are well-suited for successful treatment of incompetent perforators.

## **2.2 Study Outline**

The study's working hypothesis is that using the Venclose Vestico Catheter System for treating incompetent perforator veins (IPVs) will not result in significant adverse outcomes related to use of the device.

There will be an informed consent/consultation visit and an intervention visit. A pre-operative Duplex Ultrasound imaging will be obtained prior to or during the consultation visit. The Vestico device will be used to treat IPVs during the intervention visit. Safety assessments and pre- and post-treatment Duplex Ultrasound imaging will be obtained measuring reflux during the primary intervention. Safety assessments and post-operative Duplex Ultrasound images will be obtained within 3 days after the intervention. All subjects will be followed up at 15 days and 30-days post-operatively for a safety assessment and Duplex Ultrasound. No further study intervention, study visits or study-specific data collection will follow the 30-day follow-up. The subject population will be patients in need of treatment for Chronic venous insufficiency (CVI) and disease due to IPVs.

